11.3. Analysis Sets

11.3.1. Efficacy Analysis Sets

The full analysis set (FAS) includes all randomized subjects. Efficacy analyses will be based on the treatment allocated at randomization (as randomized).

The modified full analysis set (mFAS) includes all FAS subjects who undergo the post up-dosing DBPCFC at week 28 (visit 16 with a window of -7/+30 days) or discontinue from study prior to week 28 (visit 16 with a window of -7/+30 days).

The mFAS will be used for primary analysis for all efficacy endpoints. Analysis of the FAS will also be done for supportive analyses.

11.3.2. Safety Analysis Set

The safety analysis set (SAF) includes all randomized subjects who received any study drug; it is based on the treatment received (as treated). Treatment compliance/administration and all clinical safety variables will be analyzed using the SAF.

11.3.3. Other Analysis Sets

The pharmacokinetic population includes all treated subjects who received any study drug and who had at least 1 non-missing drug concentration result following the first dose of study drug.

The ADA analysis set includes all treated subjects who received any study drug and who had at least 1 non-missing ADA result following the first dose of study drug.

The NAb analysis set includes all treated subjects who received any study drug and who are negative in the ADA assay or with at least 1 non-missing result in the NAb assay (subjects who are ADA negative are set to negative in the NAb analysis set).

11.4. Statistical Methods

For continuous variables, descriptive statistics will include the following information: the number of subjects reflected in the calculation (n), mean, median, first quartile (Q1), third quartile (Q3), standard deviation, minimum, and maximum.

For categorical or ordinal data, frequencies and percentages will be displayed for each category.

All data will be summarized by treatment groups as outlined below:

- Double-blind treatment period with pre-dosing and up-dosing of AR101 (28 to 40 weeks): placebo plus AR101 vs dupilumab plus AR101.
- Double-blind maintenance phase (24 weeks): continuously on placebo + AR101, previously on dupilumab + AR101 and re-randomized to placebo + AR101, continuously on dupilumab + AR101.

Regeneron Pharmaceuticals, Inc.

11.4.1. Subject Disposition

The following will be provided:

- The total number of screened subjects: met the inclusion criteria regarding the target indication and signed the ICF
- The total number of randomized subjects: received a randomization number
- The total number of subjects in each analysis set (eg, mFAS, FAS defined in Section 11.3.1 for all efficacy analysis sets)
- The total number of subjects who discontinued the study, and the reasons for discontinuation
- A listing of subjects treated but not randomized, subjects randomized but not treated, and subjects randomized but not treated as randomized
- A listing of subjects prematurely discontinued from treatment, along with reasons for discontinuation

11.4.2. Demography and Baseline Characteristics

Demographic and baseline characteristics will be summarized descriptively by treatment group, and by all subjects combined.

11.4.3. Efficacy Analyses

The primary efficacy analyses for all the efficacy endpoints will be conducted using the mFAS population. As supportive evidence, the same analysis approach will be repeated with the FAS population.

11.4.3.1. Primary Efficacy Analysis

The primary endpoint will be analyzed using the Cochran-Mantel-Haenszel test adjusted by randomization stratification factors to assess the treatment difference in the proportion of responders (ie, those who "pass" a post up-dosing DBPCFC with 2044 mg [cumulative] peanut protein at visit 16 [week 28 with a visit window of -7/+30 days]) in the mFAS. Estimate of treatment difference, p-value, and the 2-sided 95 % confidence interval will be provided.

In addition, the primary efficacy endpoint will be performed on the FAS as a supportive analysis.

If a subject does not have available post up-dosing DBPCFC data at visit 16, the subject will be considered as a non-responder regardless of reasons for missing data.

Sensitivity analyses will include an analysis of the subset of subjects with available post up-dosing DBPCFC data from visit 16.

Subgroup analysis (eg, by baseline weight group) will also be performed.

11.4.3.2. Secondary Efficacy Analysis

Continuous Endpoints at Visit 16

Change in the cumulative tolerated dose (log transformed) of peanut protein during a post up-dosing DBPCFC from baseline at visit 16 will be analyzed using analysis of covariance (ANCOVA) with treatment as the main effect, stratification variables and baseline tolerated cumulative amount of peanut protein DBPCFC as covariates. In addition, a non-parametric analysis using the Van Elteren test will be conducted to assess the sensitivity to the assumption about normality of response variable as required by ANCOVA.

If a subject does not have an available post up-dosing DBPCFC at visit 16, their baseline value will be used to impute the missing DBPCFC data at visit 16 (ie, baseline observation carried forward). Sensitivity analysis using complete cases will be conducted to assess the robustness of the result, with regard to handling of missing data. Other sensitivity analyses may be conducted and will be specified in the SAP.

Continuous secondary efficacy endpoints that are measured repeatedly over time during the 28 to 40 week double-blind treatment period (eg, EASI) will be analyzed using ANCOVA in a similar way to the endpoint of change in the cumulative tolerated dose of peanut protein. For these endpoints, missing data will be imputed by multiple imputations.

Endpoints at Visit 22 or 25

Secondary endpoints at visit 22 (the end of the maintenance period) or at visit 25 (the end of study) will be analyzed descriptively at given visits. These descriptive analyses may include statistical tests depending on the type of data in the same way as described above.

11.4.3.3. Multiplicity Considerations

The overall Type-1 error rate of 0.05 (2-sided) will be controlled for the primary endpoint and the first secondary endpoint (ie, change in the cumulative tolerated dose [log transformed] of peanut protein during a post up-dosing DBPCFC from baseline to visit 16) using a hierarchical testing procedure. Inferential conclusions about the first secondary endpoint require statistical significance at the 2-sided 0.05 significance level of the primary endpoint.

11.4.3.4. Timing of Analyses

A primary analysis may be performed when the last subject completes 28 to 40 weeks of the double-blind treatment period as specified in the protocol (visit 16 or earlier for those subjects who are withdrawn prematurely from the study). No changes in the conduct of the study will be made based on this primary analysis. The assessment of primary and secondary endpoints up to visit 16 as specified in Section 11.4.3.1 and Section 11.4.3.2 and performed during the analysis will be the final analysis of the primary endpoint and the secondary endpoints up to visit 16. Hence there will be no need for alpha adjustment due to the primary analysis. If a decision is made to perform the primary analysis, in order to maintain study integrity with respect to the maintenance phase and the post-treatment follow-up visits, and analyses, a dissemination plan will be written. This plan will clearly identify the team (including the statistician) that will perform the primary analysis and all related activities, restrict other clinical team members and other sponsor personnel from access to individual subject treatment allocation and site level analysis results, and ensure that the

dedicated team will not participate in the data review or data decisions for the following post-treatment analyses. However, the dedicated team can participate in the analysis following the final database lock. In addition, an end of maintenance phase analysis may be performed when the last subject completes the maintenance treatment period (week 52 to 64 visit or earlier for those who are withdrawn prematurely from the study). If a decision is made to perform the end of maintenance phase analysis, measures similar to those taken for the primary analysis will be used in order to maintain study integrity with respect to the post-treatment follow-up visits and analyses.

11.4.4. Safety Analysis

11.4.4.1. Adverse Events

Definitions

For safety variables, 2 observation periods are defined:

- The pretreatment period is defined as the time from signing the ICF to before the first dose of study drug.
- The treatment-emergent period is defined as the day from first dose of study drug to the end of the study. The treatment-emergent period includes the 28 to 40 week up-dosing treatment period, the 24-week maintenance treatment period, and the follow-up period.

Treatment-emergent adverse events (TEAEs) are defined as those that are not present at baseline or represent the exacerbation of a pre-existing condition during the treatment-emergent period.

Analysis

All AEs reported in this study will be coded using the currently available version of the Medical Dictionary for Regulatory Activities (MedDRA[®]). Coding will be to lowest level terms. The verbatim text, the preferred term (PT), and the primary system organ class (SOC) will be listed.

Summaries of all TEAEs by treatment group will include:

- The number (n) and percentage (%) of subjects with at least 1 TEAE by SOC and PT
- TEAEs by severity (according to the grading scale outlined in Section 10.5.1), presented by SOC and PT
- TEAEs by relationship to treatment (related, not related), presented by SOC and PT
- Treatment-emergent AESIs (defined with a PT or a prespecified grouping)

Deaths and other SAEs will be listed and summarized by treatment group.

Treatment-emergent adverse events leading to permanent treatment discontinuation will be listed and summarized by treatment group.

11.4.4.2. Other Safety

Vital Signs

Vital signs (temperature, pulse, blood pressure, and respiration rate) will be summarized by baseline and change from baseline to each scheduled assessment time with descriptive statistics.

CONFIDENTIAL

Page 98 of 118

The number and percentage of subjects with a treatment-emergent potentially clinically significant value (PCSV) will be summarized for each vital sign variable. The criteria for treatment-emergent PCSV will be defined in the SAP.

Laboratory Tests

Laboratory test results will be summarized by baseline and change from baseline to each scheduled assessment time with descriptive statistics.

Number and percentage of subjects with a treatment-emergent PCSV at any post-randomization time point will be summarized for each clinical laboratory test. The criteria for treatment-emergent PCSVs will be defined in the SAP.

Shift tables based on baseline normal/abnormal and other tabular and graphical methods may be used to present the results for laboratory tests of interest.

Listings will be provided with flags indicating the out of laboratory range values.

11.4.4.3. Treatment Exposure

The duration of exposure during the study will be presented by treatment group and calculated as:

(Date of last study drug injection – date of first study drug injection) + 14 days

The number (%) of subjects randomized and exposed to double-blind study drug will be presented by specific time periods for each treatment group. The time periods of interest will be specified in the SAP.

In addition, duration of exposure during the study will be summarized for each treatment group using number of subjects, means, standard deviation, minimums, Q1, medians, Q3, and maximums.

A summary of the number of doses by treatment group will be provided.

11.4.4.4. Treatment Compliance

The compliance with study treatment will be calculated as follows:

```
Treatment compliance of study drug = (Number of study drug injections during exposure period)/(Number of planned study drug injections during exposure period) \times 100%
```

The compliance with AR101 will be calculated as follows:

Treatment Compliance of AR101 = (total actual peanut dose protein [mg] received during exposure period)/(total planned dose protein [mg] during exposure period) × 100%

The treatment compliance of study drug and AR101 will be presented by specific ranges for each treatment group. The ranges of interest will be specified in the SAP.

11.4.5. Analysis of Drug Concentration Data

Descriptive statistics will be used to summarize the concentration data at each sampling time.

Regeneron Pharmaceuticals, Inc.

CONFIDENTIAL

11.4.6. Analysis of Immunogenicity Data

- Listings of pre-existing, treatment-emergent and persistent ADA responses, titers, and NAb positivity presented by subject, time point, and dose group will be provided. Incidence of treatment-emergent and treatment-boosted ADA will be assessed as absolute occurrence (N) and percent of subjects (%), grouped by study cohorts and ADA titer level as follows:
- Pre-existing immunoreactivity, defined as a positive ADA assay response at baseline, with all post-dose ADA results negative, or a positive assay response at baseline, with all post-dose ADA assay responses less than 4-fold over baseline titer levels.
- Treatment-emergent defined as any post-dose ADA-positive response when baseline results are negative or missing.
 - Treatment-emergent ADA response may be further characterized as persistent, transient, or indeterminate.
- Treatment-boosted defined as any post-dose positive ADA response that is at least 4-fold over the baseline level when baseline is positive in the ADA assay.
- Titer category (Maximum ADA titer values)
 - Low (titer <1,000)
 - Moderate $(1,000 \le \text{titer} \le 10,000)$
 - High (titer >10,000)
 - NAb status for samples that are positive in the ADA assay

Listings of pre-existing, treatment-boosted, and treatment-emergent ADA responses, ADA titers and NAb positivity presented by subject, time point, and dose cohort/group will be provided. Incidence of treatment-emergent ADA and NAb will be assessed as absolute occurrence (N) and percent of subjects (%), grouped by study cohorts and ADA titer level.

Plots of drug concentrations will be examined and the influence of ADAs and NAbs on individual PK profiles evaluated. Assessment of impact of ADA and NAbs on safety and efficacy may be provided.

11.4.7. Analysis of Pharmacodynamic Data

The exploratory biomarker data will be summarized by descriptive statistics.

11.5. Additional Statistical Data Handling Conventions

The following analysis and data conventions will be followed:

Definition of baseline:

• The baseline assessment will be the latest, valid pre-first-dose assessment available.

General rules for handling missing data:

• Rules for handling missing data for assessment (other than efficacy)

CONFIDENTIAL

Page 100 of 118

- If the start date of an AE or concomitant medication is incomplete or missing, it will be assumed to have occurred on or after the intake of study medication, except if an incomplete date (eg, month and year) clearly indicates that the event started prior to treatment. If the partial date indicates the same month or year of the intake of study medication date, then the start date by the study medication intake date will be imputed; otherwise, the missing day or month by the first day or the first month will be imputed.
- No imputations for missing laboratory data, vital sign data, or physical examination data will be made.

Visit windows:

• Assessments taken outside of protocol allowable windows will be displayed according to the case report form (CRF) assessment recorded by the investigator.

Unscheduled assessments:

• Extra assessments (laboratory data or vital signs associated with nonprotocol clinical visits or obtained in the course of investigating or managing AEs) will be included in listings, but not summaries. If more than 1 laboratory value is available for a given visit, the first observation will be used in summaries, and all observations will be presented in listings.

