3.3. The Safety Analysis Set (SAF)

SAF includes all randomized subjects who receive at least one injection of dupilumab/placebo and be analyzed as treated. Treatment assignment will be based on the actual treatment received not the treatment assigned by IWRS randomization. Treatment compliance/administration for investigational product including both dupilumab/placebo and AR101, as well as all clinical safety variables will be summarized based on SAF.

For the safety analyses during the maintenance period, a subset of SAF which is defined as SAF-maintenance includes re-randomized subjects at visit 16 who received at least one injection of dupilumab/placebo during the maintenance period. Treatment compliance/administration for investigational product and all clinical safety variables during maintenance period will be summarized based on SAF-maintenance.

The actual treatment group as treated is defined by the following rule:

- For a subject randomized to dupilumab Q2W (any dose level), if the subject received all placebo injections, the actual treatment will be assigned as placebo.
- Regardless of the treatment group a subject is randomized to, if the subject received at least 1 dupilumab injection, the actual treatment will be assigned as dupilumab Q2W (any dose level).

For safety summaries, the analysis periods are defined as follows:

- Pre-dosing period (4 weeks) is defined as:
 - Day 1 to the day before the date of AR101 IDED in the up-dosing period if subjects completed the IDED at Week 4
 - Day 1 to early termination (ET) visit date before Week 4 if subjects early terminated from the pre-dosing period
- Up-dosing period (24 to 36 weeks) is defined as:
 - For subjects who entered maintenance period: The date of AR101 IDED to the date of second post up-dosing DBPCFC at visit 16.
 - For subjects who did not enter maintenance period:
 - The date of AR101 IDED at Week 4 to the date of visit 16 if subjects entered follow-up period
 - The date of AR101 IDED at Week 4 to the last dose date of dupilumab/placebo + 14 days if subjects completed dosing to visit 16 but did not enter follow-up period
 - The date of AR101 IDED at Week 4 to early termination (ET) visit date before visit 16 if subjects did not complete dosing to visit 16
- Maintenance period (24 weeks) for subjects who entered maintenance period is defined as:

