5.3. Prior and Concomitant Medications/Procedures

Number and proportion of subjects taking prior/concomitant medications, prohibited medications and rescue medications will be summarized for each treatment group and study total based on the SAF and SAF-maintenance by ATC level 2 and ATC level 4, sorted by decreasing frequency of ATC level 2 and ATC level 4 based on the overall incidence for the combined treatment groups for each study period.

CONFIDENTIAL

Page 36 of 86

Number and proportion of subjects taking prior/concomitant procedures will be summarized for each treatment group and study total based on the SAF and SAF-maintenance, sorted by decreasing frequency of SOC and PT based on the overall incidence for the combined treatment groups for each study period.

In addition, the summary of prior/concomitant medications/procedures will be performed for subjects who were impacted by COVID-19 pandemic and not impacted by COVID-19 pandemic in each study period, respectively. The summary will be performed for pre-, during, and post-COVID-19 periods for subjects impacted by COVID-19, if applicable.

Number and proportion of subjects taking at least one epinephrine and short-term use of systemic corticosteroids for treatment of acute-allergic reactions will be summarized during the following periods,

- Screening DBPCFCs of peanut protein
- Week 4 IDED
- Post up-dosing DBPCFCs of peanut protein
- Post maintenance DBPCFCs of peanut protein
- End of study DBPCFCs of peanut protein

The number of episodes of epinephrine use and short-term use of systemic corticosteroids during up-dosing period (excluding post up-dosing DBPCFCs) and during maintenance period (excluding post maintenance DBPCFCs) will be summarized, respectively.

Kaplan-Meier curves for time to first rescue treatment use will be created for each study period.

Listing of pre-treatment and concomitant medications will include generic name, ATC levels 2 and 4, indication, the study day of onset (for medications started before treatment, the study day of onset = date of medication start – date of the first dose; for medication started on or after treatment, the study day of onset = date of medication start – date of the first dose + 1), the study day of medication end date, ongoing status, dose, frequency, and route.

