6.3. Data Handling Convention for Missing Data

Missing data will not be imputed in listings. This section includes the methods for missing data imputation for some summary analyses, if necessary.

Adverse event

If the intensity of a TEAE is missing, it will be classified as "severe" in the frequency tables by intensity of TEAE. If the assessment of relationship of a TEAE to the investigational product is missing, it will be classified as "related" in the frequency tables by relation to the investigational product.

Adverse event start date

AE start date will be used for AE classification and analysis of AESIs. If AE start date is not complete, then the character variable will keep the original incomplete date, the numerical date variable will be imputed, and an imputation flag will indicate which date component is missing.

If AE start day is missing, and AE start month and year are not missing: If AE start year is the same as first dose year and the AE start month is the same as the first dose month, then impute AE start day using the day of first dose. If this leads to a date after the AE end date, use AE end date instead. Otherwise impute the AE start day using the first day of the month. If this leads to a date before informed consent, the informed consent date will be used. Imputation flag is 'D'.

If AE start month is missing, and AE start year is not missing: If AE start year is before the first dose year, use the informed consent day and month. If AE start year is equal to the first dose year, use the first dose day and month. If this leads to a date after the AE end date, use AE end date instead. If AE start year is after the first dose year, use 01 January. Imputation flag is 'M'.

If AE start year is missing: Impute AE start date using the date of first dose. If this leads to a date after the AE end date, use AE end date instead. Imputation flag is 'Y'.

Adverse event end date

The general recommendation is not to impute AE end date. However, since AE end date will be used for AE starting date imputation, to carry through the logic for programming, the following intermediate step will be used. Afterwards, only the original character/numeric date recorded in CRF will be kept in the final analysis dataset.

If AE end day is missing, and AE end month and year are not missing: Impute AE end date using the last day of the month. If this leads to a date after end of study follow up date, use end of follow up date instead.

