If AE end month is missing, and AE end year is not missing: Impute AE end date using 31 December as the day and month. If this leads to a date after end of study follow up date, use the end of follow up date instead.

If AE end year is missing: Impute AE end date using the end of follow up date.

Prior or concomitant medication

Medication start and end date missing

To determine whether a medication is prior medication or concomitant medication or both, the missing medication start date is estimated as early as possible, and the missing medication end date is estimated as late as possible. If the medication start date is missing, the onset day will not be calculated in medication listings.

Prior medication start date

If start day is missing, and start month and year are not missing: Impute the start day using the first day of the month. Imputation flag is 'D';

If start month is missing, and start year is not missing: Impute the day and month using 01 January. Imputation flag is 'M'.

If start year is missing: Impute start date using 2 years before inform consent date. Imputation flag is 'Y'.

A special note: for start date with year missing, the general principle is not to impute. However, to simplify the programming flow, the imputation is proposed to align with the protocol which specifies to collect up to 2 years prior medication. Since the start date of prior medication will not be used in any analysis, the rule will not impact the analysis result.

Prior medication end date

If end day is missing, and end month and year are not missing: Impute end date using the last day of the month. If this leads to a date on or after first dose intake date, use first dose intake date -1 instead. Imputation flag is 'D'.

If end month is missing, and end year is not missing: Impute end date using 31 December as the day and month. If this leads to a date on or after first dose intake date, use first dose intake date -1 instead. Imputation flag is 'M'.

If end year is missing: Impute end date using the first dose intake date -1. Imputation flag is 'Y'.

Concomitant medication start date

The imputation rule for concomitant medication start date is the same as AE start date.

Concomitant medication end date

If end day is missing, and end month and year are not missing: Impute end date using the last day of the month. If this leads to a date after end of study follow up date, use end of follow up date instead. Imputation flag is 'D'.

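### SAP 6.3 sets AE and medication start dates with no year, or no month in the first-dose year, to the first injection, which places AR101-phase records in the pre-dosing period

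*Protocol*

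**What the plan says.** Protocol 11.5 moves a partial start date to study medication intake when it falls in the "same month or year of the intake of study medication date, then the start date by the study medication intake date will be imputed". For other partial dates, "otherwise, the missing day or month by the first day or the first month will be imputed".

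SAP 6.3 is more detailed:
- Year missing: the date of first dose.
- Month missing: "If AE start year is equal to the first dose year, use the first dose day and month". In a later year, 01 January.
- Only the day missing: if month and year both match the first dose, "then impute AE start day using the day of first dose". In any other month, the first of that month.

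For medication, "The imputation rule for concomitant medication start date is the same as AE start date". The rule's only guards are the AE end date and the informed consent date.

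SAP 6.3 also states the purpose: "AE start date will be used for AE classification and analysis of AESIs". SAP 3.3 defines the pre-dosing period as "Day 1 to the day before the date of AR101 IDED in the up-dosing period if subjects completed the IDED at Week 4". SAP 5.7.1 tabulates TEAEs separately by period, and SAP 4.3 splits concomitant medication by period. SAP 5.3 counts epinephrine and short-term systemic steroid episodes in up-dosing and adds that "Kaplan-Meier curves for time to first rescue treatment use will be created for each study period". SAP 5.7.2 summarizes anaphylaxis by period and measures time to first AESI from the first dose.

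**The concern.** First-dose imputation is cautious for one question: is the event treatment-emergent? It answers yes when in doubt. The SAP uses the same imputed date for a second question: in which study period did the event start? There the rule is not cautious. It takes records out of up-dosing, where tolerability of AR101 with and without dupilumab is judged, and puts them in the period that should show dupilumab or placebo alone. An AESI imputed to the first dose enters the time-to-event analysis at day 1.

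The guards do not help. The end-date guard can only move a date earlier, and the consent guard only keeps it from falling before consent. Neither refers to the IDED, to AR101 exposure or to the study period.

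Period also determines the label in maintenance. SAP 5.7 presents safety by the treatment received in each period. For a subject re-randomized from dupilumab to placebo, a maintenance event moved back across visit 16 is counted under dupilumab + AR101 instead of under the re-randomized placebo group.

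These tables carry added weight because SAP 1.2.3 removed the e-diary tolerability endpoints from the secondary list for low compliance.

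**Working it through.** The documents state no rate of incomplete dates, so there is no plan figure to reproduce. The check applies the rule to true up-dosing events.

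**Inputs.** IDED 28 days after the first injection (Week 4). Up-dosing ends at week 28 (28 to 196 days after injection, 169 days) or week 40 (28 to 280 days, 253 days). Assumptions: first injections spread evenly over a 365-day year, events spread evenly over up-dosing, AE end date not binding.

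**Year missing.** Every event goes to the first injection: 100%.

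**Month missing.**
- An event k days after injection falls in the first-dose year with probability (365 − k)/365. The mean k is (28 + 196)/2 = 112 or (28 + 280)/2 = 154. The share set to the first injection is 253/365 = 69.3% or 211/365 = 57.8%.
- Otherwise the date is 01 January. This precedes the IDED when the injection falls on one of 27 late-December or early-December dates (IDED after 01 January): 27/365 = 7.4%.
- Total re-dated to pre-dosing: 76.7% (week 28) or 65.2% (week 40).

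**Only the day missing.** An event moves if it falls in the IDED's calendar month and the IDED is not on the first. For a month of L days, summing over possible IDED days gives L(L − 1)/2. Over the year: (7 × 465 + 4 × 435 + 378)/365 = 5373/365 = 14.7 days. The share is 14.7/169 = 8.7% or 14.7/253 = 5.8%. Only about 0.1% land on the first injection itself.

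Full enumeration of injection dates and event days gave the same results:

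| Missing part | Up-dosing to week 28 | Up-dosing to week 40 |
|---|---|---|
| Year | 100% | 100% |
| Month | 76.7% | 65.2% |
| Day only, SAP 6.3 | 8.7% | 5.8% |
| Day only, Protocol 11.5 read literally | 70.1% | 58.3% |

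The last row differs because the protocol accepts a match on month or year, while the SAP requires both when only the day is missing.

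**Example.** First injection 11 March, IDED 8 April.
- True start 15 June: a missing day gives 1 June (correct period); a missing month or year gives 11 March (pre-dosing).
- True start 20 April: a missing day gives 1 April, a week before the IDED.

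**Maintenance.** The first-of-month arithmetic also applies at visit 16. With 24 × 7 = 168 days of maintenance, 14.7/168 = about 9% of events with only the day missing would fall back into up-dosing.

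**The case against.** The strongest reply is that few records and few tables are touched.

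- *Day-only gaps mostly survive.* A reader might infer that all incomplete dates go to the first injection. SAP 6.3 does not say that: 91 to 94% of up-dosing events missing only the day stay in the right period.
- *The protocol's own analysis is not harmed.* Protocol 11.4 summarizes pre-dosing and up-dosing together, so a shift between them changes nothing there. SAP 1.2.3 introduced the separate 4-week summary. The gap is therefore in SAP 6.3.
- *Many peanut reactions bypass the rule.* Protocol 10.4.1 records reactions to challenges, in-clinic AR101 and home dosing as allergic signs and symptoms. SAP 5.3 tabulates epinephrine and steroid use at the IDED and challenges by occasion, and SAP 4.4 has one acute-treatment category that pools pre-dosing with up-dosing.
- *Incomplete months should be rare.* Up-dosing visits are every two weeks with AE and medication review, and sites telephone the day after each in-clinic up-dose or challenge.
- *Some traceability exists.* SAP 6.3 keeps the original partial date and sets D/M/Y flags.
- *The rule ignores treatment arm.* A reader might infer bias between arms; the rule alone does not create it.

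All of this stands and limits the size. It does not remove the problem for ordinary AEs, anaphylaxis by period, up-dosing counts of epinephrine and steroid episodes, per-period rescue curves, or time to first AESI.

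**Conclusion.** The concern holds for SAP 6.3, mainly for dates missing the month or year. For those the rule usually puts a true up-dosing record in a period when no AR101 had been taken: always if the year is missing, and in about 65 to 77% of cases if the month is missing. For day-only gaps the figure is about 6 to 9%. These shares assume even timing of injections and events and an IDED exactly 28 days after injection. They are shares of incomplete records, not of all events. The number of such records is not given and is probably small, so the effect on any table cannot be stated.

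The error is misplacement between periods. The documents do not support the stronger readings that the rule biases the comparison between arms or that most AR101 reactions are misdated. The point is modest but worth settling before database lock.

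**What to change.** In SAP 6.3:

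1. Keep first-dose imputation only for the treatment-emergent yes/no flag.
2. For period tables and time-to-event analyses, use the earliest date consistent with the partial date and other recorded information. It should not precede the IDED if the AE is assessed as related to AR101 or carries an action taken with AR101; SAP 5.7.1 already lists both fields. It should not precede the preceding visit where the CRF captures the visit of first report. The documents do not show that it does, so this bound is conditional.
3. Mark imputed records in the period tables with the existing D/M/Y flags.
4. Add a sensitivity tabulation that assigns ambiguous records to the later compatible period. This covers medication records, for which the SAP 5.3 listing shows no AR101 relationship field, and AEs that began before the IDED but later led to an AR101 action.
5. Reconcile the protocol's month-or-year wording in 11.5 with the SAP's month-and-year rule for day-only gaps.

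The cost is a few lines of text, minor programming and one extra tabulation.
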